**Study Protocol:**

**Study Timeline**

Study Visit Timeline	Visit 1	Visit 2	Visit 3	Visit 4	Visit 5	Visit 6 (1-month follow up)
Consent	X					

Clinical Evaluation	X				X	X
Tasks/Cognition Testing	X				X	X
EEG	X				X	X
tES	X	X	X	X	X	
Sensation Questionnaire	X	X	X	X	X	
Self-Reports	X				X	X

## **Study Visits and Details:**

Participants will complete baseline clinical, neuropsychological, visuoperceptual and neuro-physiological assessments (day 0), short-term follow-up (day 5) and long-term follow-up (month 1).

### **Pre-Screening**

Subjects will be prescreened. If the subject appears to qualify for the study, they will be invited in for a screening and a baseline visit.

### **Screening and Baseline Procedures (approximately 3-4 hours)**

Screening and baseline procedures will be conducted in the Massachusetts Mental Health Center (MMHC)/ Beth Israel Deaconess Medical Center (BIDMC) in Boston, MA. The urine toxicology screen and pregnancy test will be completed at MMHC or within BIDMC.

- Eligibility pre-screen will include a telephone pre-screening questionnaire that will assess basic inclusion and exclusion criteria.

- Eligibility screening will include a screening questionnaire that will assess more details related to inclusion and exclusion criteria and will be conducted in-person during the clinical diagnostic session (i.e., the first visit to the laboratory).

- Informed consent will be obtained

- Urine toxicology screen

- Urine pregnancy testing for females of childbearing age

**Subjects will be informed that if they do not pass the urine toxicology screen (other than prescribed medication), they will be withdrawn from the study and will not receive compensation for the initial visit. This will be made clear in the pre-screening questionnaire.**

- tES screening questions for tES participation

- Demographics: Subjects will be asked to provide standard demographic information (age, sex, race/ethnicity, level of education, cohabitation status) using forms employed in previous studies.

- Psychiatric, medical, substance use history and medication review

- Signing a release to allow for access to recent psychiatric records, if confirmation of medications or psychiatric history is necessary

## **OBJECTIVES**

### **Primary Objective**

The primary objective of this study is to evaluate the effectiveness of tDCS for improving the positive and general symptoms associated with individuals who have a history of hallucinations (PANSS, UMPDH-Q and AHRS).

### **Secondary Objectives**

The secondary objective of the study is to evaluate the safety and tolerability of tDCS targeting the rSTS as well as secondary clinical outcomes including depression, mania, cognition, sensory integration, electrophysiology outcomes and global functioning

**Clinical and Cognitive Outcomes:** Symptom ratings will be collected using the PANSS, UMPDH-Q, AHRS, YMRS, MADRS, GAF, SCL-90 and cognition with the BAC

**Electrophysiology Outcomes:** A steady state evoked task will be implemented probing the auditory, visual and audiovisual integration capacity of mechanisms linked to the rSTS.

**Computerized behavioral tasks:** The biological motion task will be used to determine the effective targeting of the rSTS and prevention of off target stimulation. Lastly, to investigate the behavioral outcomes related to visual/audio perceptual functions, the NES will be employed to determine effective auditory and visual integration abilities.

### **Diagnostic Assessments**

#### **Structured Clinical Interview for DSM-IV (SCID)**

This is a structured clinical diagnostic screening interview for subjects 15 and older. It is used to diagnose Axis I disorders including modules on depression, mania, psychosis, alcohol and substance use, anxiety, somatic and eating disorders.

### **Clinical Assessments**

#### **Positive and Negative Symptom Scale (PANSS)**

The ratings are based on a clinical interview conducted by trained clinical staff, covering all of the items on the rating scale.

- This rating scale is meant to capture many different types of symptoms including positive, negative, and general psychopathology symptoms. The ratings are based on a clinical interview with the participants.
- Ratings should be based on the patient's condition in the past week.
- Always use the manual with anchor points when scoring and do not try to score from your memory of the anchor points or by their headings (mild, moderate or severe).

#### **University of Miami Parkinson's Disease Hallucinations Questionnaire (UMPDH-Q)**

Administer questions on severity of hallucinations (1-6) and questions of quality of hallucinations (7-20). Each hallucination type (e.g. visual, auditory, tactile, olfactory) experienced derives an individual score. Higher total scores mean worsening symptoms.

### **Auditory Hallucinations Rating Scale (AHRS)**

A short 7-item clinician-rated scale measuring severity, frequency, duration, loudness, impact and distress level of auditory hallucinations presently experienced. Higher total scores mean worsening symptoms.

### **Montgomery and Asberg Depression Rating Scale (MADRS)**

#### **Interviewer:**

The questions in bold for each item ***should be asked exactly as written***. Often these questions will elicit enough information about the severity and frequency of a symptom for you to rate the item with confidence. Follow-up questions are provided; however, for use when further exploration or additional clarification of symptoms is necessary. The specified questions should be asked until you have enough information to rate the item confidently. In some cases, you may also have to add your own follow-up questions to obtain the necessary information.

*\*Ratings should be based on the patient's condition in the past week.*

**Referent of "usual" or "normal" conditions.** Several of the interview questions refer to the patient's usual or normal functioning. In some cases, such as when the patient has Dysthymia or Seasonal Affective Disorder, the referent should be to the last time they felt OK (i.e., not depressed or high) for at least a few weeks.

***\*Rate the highest level of psychopathology. When in doubt, rate up and record the higher score.***

### **Global Assessment Functioning (GAF)**

Consider psychological, social, and occupational functioning on a hypothetical continuum of mental health-illness. Do not include impairment in functioning due to physical (or environmental) limitations.

Indicate appropriate code for the **LOWEST level of functioning during the week of POOREST functioning in the past month.** (Use intermediate level when appropriate, i.e., 45, 68, 72).

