# **Improving Hallucinations by Targeting the rSTS with tES**

**NCT #: NCT05165654**

**June 13, 2025**

Protocol Number:	2019P001016X
Title:	Improving Hallucinations by Targeting the rSTS with tES
Design:	Double blind, sham controlled design with baseline, day 5 and 1 month follow up visits during which tES (cathodal tDCS or sham) was delivered to the right superior temporal sulcus (rSTS) from baseline to day 5 each day (5 days) twice a day for 20 mins. Participants were randomly assigned to either active cathodal tDCS or sham condition to test the effectiveness and feasibility of stimulating the rSTS using a novel targeting methodology consisting of a lesion network guided brain target linked to hallucinations.
Objectives:	Evaluate the effectiveness and safety of tDCS for improving the positive and general symptoms associated with individuals who have a history of hallucinations
Enrollment:	12 Individuals
Clinical Sites:	Beth Israel Deaconess Medical Center, Boston, MA
Patient Population:	Male or female outpatients 18-50 years of age patient's diagnosis with either schizophrenia, schizoaffective disorder, or psychotic bipolar as defined by DSM-5 or DSM-IV-TR criteria
Primary and Secondary Outcomes:	Primary Outcomes: Positive and Negative Syndrome Scale (PANSS); University of Miami Parkinson's Disease Hallucinations Questionnaire (UMPDH-Q); Auditory Hallucinations Rating Scale (AHRS). Secondary Outcomes: Global Assessment of Functioning (GAF); Young Mania Rating Scale (YMRS); Symptom Checklist 90 (SCL-90) Biological Motion; Steady State EEG (Visual, Auditory and Multimodal); Brief Assessment of Cognition (BAC); Montgomery-Asberg Depression Rating Scale (MADRS); Neurological Evaluation Scale (NES); Biological Motion.

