### **Secondary Endpoints**

Change from baseline to day 5 and 1 month in GAF total score after 1 week of tES. Change from baseline to day 5 and 1 month in MADRS, YMRS, SCL-90, SCL-90 after 1 week of tES. Change from baseline to day 5 and 1 month in voltage for auditory, visual and audiovisual integration steady state measures after 1 week of tES. Change from baseline to day 5 and 1 month in cognition scores after 1 week of tES.

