### **Primary Analyses**

Primary Analysis of the primary, secondary, and additional efficacy endpoints:

Mixed Model Repeated Measures analysis (MMRM)/non- parametric methods will be used to compare using within group differences as well as to determine the difference between the two treatment groups on the primary, secondary and safety endpoints depending on the distribution of the data.

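### GAF is rated on the poorest week of the past month, so its day-5 change score can show almost no benefit from five days of stimulation

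*Combined protocol and SAP*

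**What the plan says.** The section on Global Assessment Functioning (GAF) instructs the rater to code the "LOWEST level of functioning during the week of POOREST functioning in the past month". It gives no shorter window for follow-up ratings, and no other section does.

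The Secondary Endpoints section lists "Change from baseline to day 5 and 1 month in GAF total score after 1 week of tES".

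The Design row of the synopsis has stimulation delivered "from baseline to day 5 each day (5 days) twice a day for 20 mins". The Study Timeline marks tES at Visits 1 to 5 and clinical evaluation at Visits 1, 5 and 6. Study Visits and Details puts baseline at day 0, followed by "short-term follow-up (day 5) and long-term follow-up (month 1". Visit 6 is labelled "Visit 6 (1-month follow up)", without saying which visit the month is counted from.

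The Secondary Objectives include "sensory integration, electrophysiology outcomes and global functioning". The Primary Analyses section uses MMRM or non-parametric methods "to determine the difference between the two treatment groups on the primary, secondary and safety endpoints". It does not treat day-5 GAF differently.

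**The concern.** A change score can show a treatment effect only if the follow-up rating describes a period in which treatment could have acted. Here the day-5 rating looks back over a month that is mostly the same month rated at baseline, and it keeps only the worst part of it. If the worst week came before treatment, no later improvement can raise the score. A rapid deterioration can still lower it.

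GAF is the only listed measure of global functioning. A day-5 comparison close to zero could be read as evidence that tDCS does not help functioning, when the rating rule would produce that result anyway. More participants would not repair this, because the expected difference itself is nearly removed.

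**Working it through.** The plan gives no power, effect size or SD for GAF, so there is no figure of its own to reproduce.

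**Step 1: days in the window (no assumption about variability).** Let L be the length of the month and d the number of days from first stimulation to the rating. Visit 1 to Visit 5 on consecutive days gives d = 4; day 0 to day 5 gives d = 5. The documents do not define a month in days; L = 30 is used here.

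- Pre-treatment days: L − d = 30 − 4 = 26 (86.7%) or 30 − 5 = 25 (83.3%).
- Rolling 7-day weeks: L − 6 = 24.
- Weeks wholly before treatment: (L − d) − 6 = 20 or 19.
- Weeks wholly after first stimulation: max(0, d − 6) = 0.
- Mixed weeks: 24 − 20 = 4, or 24 − 19 = 5.

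Other month lengths change little: 17 or 18 of 22 weeks are wholly pre-treatment with L = 28, and 20 or 21 of 25 with L = 31.

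**Step 2: how much of an effect registers at day 5 (illustrative).** Assumptions: daily functioning follows an AR(1) process with SD 5 and autocorrelation 0.5, 0.8 or 0.95. The effect is 10 points in every participant, there is no rater error, and the window is 30 days. Each of 40,000 simulated paths per setting is compared with the same path untreated. The score is either the lowest 7-day mean or the lowest day within that week; the ranges cover both readings, the three autocorrelations and d = 4 or 5.

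| Course of the 10-point effect | Gain registers as | Loss registers as |
|---|---|---|
| Immediate | 0.3–0.5 | 2.4–6.6 |
| Building over 5 days | 0.2–0.4 | 0.7–4.7 |
| Building over 14 days | 0.1–0.3 | 0.2–0.9 |

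With SD from 2.5 to 10, the immediate gain registers as 0.1 to 0.9 points.

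**Step 3: the 1-month rating under the same model.** A 30-day window rated on treated day D covers treated days D − 29 to D.

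- Counted from Visit 1 (D = 30): days 1 to 30, so no pre-treatment day but the whole stimulation week. At SD 5 a 10-point gain building over 5 days registers as 7.0 to 9.3, and over 14 days as 4.9 to 6.3.
- Counted from Visit 5 (D = 34 or 35): the window starts on day 5 or 6, so at most one stimulation day. The same gains register as 10 and as 7.3 to 8.8.
- If Visit 6 falls early, at D = 28, the window starts on day −1 and holds 30 − 28 = 2 pre-treatment days. An immediate gain then registers as 8.9 to 9.3 (week mean) or 5.6 to 7.5 (lowest day).

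The 1-month rating is therefore far more responsive than the day-5 rating, but how much more depends on an anchor that the plan does not state.

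**The case against.** The strongest case on the other side accepts the window count and disputes its weight.

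- **Low power anyway.** The trial enrols 12. Assuming 6 per arm and a two-sided t-test at 0.05, 80% power needs a standardised difference of about 1.8, and power at 0.8 is 24%. A null day-5 GAF result would be likely under any look-back. This is true and limits the practical impact. But low power leaves an estimate centred on the true effect, whereas this rule moves the expected difference itself towards zero.
- **The one-sidedness holds only for fast change.** A 10-point loss building over 14 days also barely registers. This stands: for gradual change, day-5 GAF is nearly blind in both directions.
- **The 1-month endpoint is not clean either.** If the month counts from Visit 1 and daily SD is 2.5, a gain building over 14 days registers as only 3.2 to 5.0. This stands, and it is why the anchor and the limitation need stating. The day-28 case applies only if Visit 6 falls early or the two months differ in length; the plan gives no visit window.
- **The simulated ranges rest on assumed values.** They do. The conclusion rests on the count in Step 1, which uses none of them.
- **Other remedies exist.** A visit-specific MMRM can estimate the 1-month contrast with day 5 still in the model, and a shorter look-back applied at every visit, including baseline, would also reconcile the two sections. Both points are fair. The MMRM does not make the day-5 contrast informative, and a new look-back cannot be applied to ratings already made.

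**Conclusion.** The concern holds. Followed as written, the plan produces a day-5 GAF comparison that is close to zero even if tDCS improves functioning. That follows from the scoring rule and the visit schedule alone: no week in the day-5 window lies wholly after first stimulation, and 19 or 20 of 24 lie wholly before it (30-day month). The size, about 0.3 to 0.5 points registered from an immediate 10-point gain, depends on the assumed SD of 5 and autocorrelation of 0.5 to 0.95; it stays below 1 point for SD 2.5 to 10.

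The consequence is confined to one secondary measure. The rule does not touch PANSS, UMPDH-Q or AHRS, and the 1-month GAF rating is affected much less. The sponsor should correct this, but it does not undermine the primary objective.

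**What to change.** In the Secondary Endpoints section:

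1. Make change from baseline to 1 month the GAF endpoint for inference.
2. Keep day-5 GAF, but report it descriptively, outside the between-group GAF test, and state that its look-back is mostly pre-treatment.
3. State whether 1 month counts from Visit 1 or Visit 5, and report the days from Visit 1 to Visit 6 for each participant.
4. State as a limitation that 1-month GAF can still understate a gradual gain, because the stimulation week or a few pre-treatment days may remain in its window.

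The cost is wording only: no new visits, staff or rating forms, and all ratings stay usable. GAF loses one inferential time point. The synopsis is partly in the past tense ("Participants were randomly assigned to either active cathodal tDCS or sham condition"), so ratings may already exist. If so, the change, its date and whether unblinded data had been seen must be disclosed, to avoid a concern about selective reporting.

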### **Young Mania Rating Scale (YMRS)**

#### ***General Instructions to the Clinician:***

The purpose of each item is to rate the severity of that abnormality in the patient. When several keys are given for a particular grade of severity, the presence of only one is required to qualify for that rating.

The keys provided are guides. One can ignore the keys if that is necessary to indicate severity, although this should be an exception rather than a rule.

Scoring between the points given (whole or half points) is possible and encouraged after experience with the scale is acquired; this is particularly useful when severity of a particular item in a patient does not follow the progression indicated by the keys.

### **Symptom Checklist 90**

Self-report questionnaire for assessing psychological distress and symptoms. It consists of 90 items that measure nine primary symptom dimensions, including somatization, obsessive-compulsive, interpersonal sensitivity, depression, anxiety, hostility, phobic anxiety, paranoid ideation, and psychotism. Each item is rated on a scale from 0 (Not at all) to 4 (Extremely). The SCL-90-R also includes three global indices: Global Severity Index, Positive Symptom Distress Index, and Positive Symptoms Total.

### **Brief Assessment of Cognition in Schizophrenia (BACS)**

Instructions (Atkins et al. 2017):

#### ***Verbal Memory (Verbal Memory & Learning Domain): 7 min***

Subjects hear a list of 15 words to remember. Words are presented by the App at a standard rate.

- Outcome measure: Total number of words recalled across 5 learning trials.

#### ***Digit Sequencing (Working Memory Domain): 5 min***

Subjects are presented with randomly ordered auditory clusters of numbers (i.e., 936) with steadily increasing trial length. Items are presented by the App at a standard rate. Subjects are asked to report the numbers in order, from lowest to highest.

- Outcome measure: Number of trials with all items in the correct order.

#### ***Token Motor Task (Motor Function): 3 min***

Subjects are presented with a virtual bowl and a supply of virtual tokens and asked to swipe a token from each side of the tablet with the index finger from each hand simultaneously and release them into the center container as rapidly as possible for 60 s.

- Outcome measure: Number of tokens correctly dragged into the container.

#### ***Semantic Fluency & Letter Fluency Tasks (Verbal Fluency Domain): 5 min***

During Semantic Fluency, subjects are given 60 s to generate as many words as possible within the category: *Animals*. Subjects are asked to generate as many words as possible beginning with a given letter. Subjects are administered two trials using letters F and S.

- Outcome measures: Total words generated for each fluency task in addition to total scores from both tasks combined to produce the Verbal Fluency domain score.

***Symbol Coding (Speed of Processing): 3 min***

Subjects assign numbers to non-meaningful symbols with the use of a key that is provided. Numbers are entered on the digital keypad and appear in the location below the corresponding symbol. Following instructions and practice, subjects are given 90 s to complete as many items as possible.

- Outcome measure: Number items completed correctly within the 90 second test period.

***Tower of London (Executive Functions/Reasoning and Problem Solving): 7 min***

Subjects are shown 2 images presented on opposite sides of the tablet screen. Each image shows a different configuration of 3 colored balls arranged on 3 pegs. The subject is required to accurately determine total number of times the balls in one picture would have to be moved in order to make the arrangement of balls identical to that of the other, opposing picture, while employing the standard rules employed in tower tests (balls are moved one at a time and balls on top of other balls must be moved first).

- Outcome measure: Number of correct responses.

[figure not shown]
**Self-Report tES Sensation Questionnaire**

Given a participant after each tES session (2x20min), the questionnaire measures severity of sensations felt during the stimulation. Rated on a scale from 0 (none) to 4 (severe). In addition, the questionnaire has an open-ended question to allow participants to express any additional sensations felt during stimulation.

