### **Safety and Tolerability Endpoint**

A self-rated questionnaire related to sensations of tES is given to participants after each stimulation.

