### **General Statistical Considerations**

All collected study data will be collected on Redcap and processed using R and Matlab software. Descriptive statistics (n, mean, standard deviation, median, minimum and maximum) will be calculated by treatment group and sham group for continuous variables.

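### The only stated safety endpoint has no planned count of participants by severity and no planned listing of free-text reports; its unit of summary is also unstated

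*Combined protocol and SAP*

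**What the plan says.** All references are to the combined protocol and SAP.

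- **Endpoint.** The section Safety and Tolerability Endpoint consists of one sentence: "A self-rated questionnaire related to sensations of tES is given to participants after each stimulation". It derives no variable from the questionnaire, such as a worst score, a threshold or a count.
- **Content.** The section Self-Report tES Sensation Questionnaire describes ratings from 0 (none) to 4 (severe) and adds that "the questionnaire has an open-ended question to allow participants to express any additional sensations felt during stimulation".
- **Descriptive summary.** General Statistical Considerations states: "Descriptive statistics (n, mean, standard deviation, median, minimum and maximum) will be calculated by treatment group and sham group for continuous variables". It does not say whether the 0 to 4 ratings count as continuous, or whether the unit is the participant, the session or the pooled record.
- **Comparison.** Primary Analyses states: "Mixed Model Repeated Measures analysis (MMRM)/non- parametric methods will be used to compare using within group differences". The same sentence extends these methods to differences between groups and to the safety endpoints.

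Safety and tolerability are a secondary objective, and safety also appears in the synopsis objective. The text provided has no section on recording or reporting adverse events.

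**The concern.** A reader of the tolerability result wants to know how many people in each arm had a severe sensation, and which sensations occurred that the form does not list. The methods named answer neither question. A mean or median rating is not a count of people. The maximum shows that a 4 occurred in the arm, but not in how many participants. Free text has no numeric value, so it cannot enter a continuous summary, an MMRM or a rank test.

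Because the form is completed repeatedly, the unit of summary decides whether a reaction confined to one person can be told apart from a reaction that everyone had. The trial tests a novel targeting method, so the open-ended item is of direct interest.

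**Working it through.** **Inputs**

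- Enrolment: "12 Individuals" (synopsis).
- Allocation: "Participants were randomly assigned to either active cathodal tDCS or sham condition" (synopsis). No ratio is given, so 6 per arm is an assumption; 4 to 8 was also checked.
- Stimulations: "from baseline to day 5 each day (5 days) twice a day for 20 mins" (synopsis), so 5 × 2 = 10 per participant.
- Questionnaires: ten each if one follows every stimulation. The wording "Given a participant after each tES session (2x20min), the questionnaire measures severity of sensations felt during the stimulation" could also mean one per day, which gives five. Both were checked.

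The plan states no reaction rate or safety precision, so there is no figure of its own to reproduce.

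**Two constructed cases: one item, one arm of 6, ten questionnaires each, ratings of 0 or 4**

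- Case A: one participant rates 4 at six sessions.
- Case B: six participants rate 4 once each, at six different sessions.

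**Pooled records.** Both cases have 60 records, six of them equal to 4. Mean = 24/60 = 0.40. Variance = (6 × 16 − 60 × 0.40²)/59 = 86.4/59 = 1.464, so SD = 1.21. Median 0, minimum 0, maximum 4. All six planned statistics are identical.

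**By session (n = 6 each).** In both cases, six sessions contain a single 4: mean 4/6 = 0.67, SD = √[(16 − 6 × 0.667²)/5] = 1.63, median 0, maximum 4. The other four sessions are all zero. The tables are identical at all ten sessions.

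**One value per participant**

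| Summary (n = 6) | Case A | Case B |
|---|---|---|
| Worst rating: mean, SD, median, min, max | 0.67, 1.63, 0, 0, 4 | 4.0, 0, 4, 4, 4 |
| Participant mean: mean, SD, median, min, max | 0.40, 0.98, 0, 0, 2.4 | 0.40, 0, 0.4, 0.4, 0.4 |

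Here the cases separate. With one worst rating per participant and arm sizes of 4 to 8, a single reactor gives a mean of 1.0 down to 0.5, never 4.

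**Five questionnaires each (30 records).** Pooled summaries can still coincide for one versus six participants with a 4.

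- First set: one participant rates 4 five times, a second rates 3 three times, and a third rates 1 once.
- Second set: all six rate 4 once, and three of them also rate 2 once.
- Both sum to 30 with a sum of squares of 108, so mean = 1.00 and SD = √[(108 − 30)/29] = 1.64. Median 0, minimum 0, maximum 4.

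Tables by day can match for one versus five reactors, with one severe rating per day.

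**Count of participants with a worst rating of 4.** Case A: 1/6 = 16.7% (exact 95% CI 0.4% to 64.1%). Case B: 6/6 = 100% (54.1% to 100%). The count separates the cases however often the form is completed.

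**The case against.** The strongest reply is that the plan never says it pools sessions. A reader might infer pooling from the repeated questionnaires, but the unit is simply not given, and with one value per participant the planned statistics tell the two cases apart. This stands, so the matching summaries are a conditional result.

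The planned comparison of safety endpoints could also help. An MMRM models correlation within a person, and in the example any two affected sessions correlate +1 in Case A and −0.2 in Case B. A rank test of participant means against an all-zero sham arm of 6 (an assumption) gives exact two-sided p = 1.0 in Case A and 2/924 = 0.002 in Case B. That is right, but a p-value or a difference in mean ratings still does not report how many people were affected.

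The example is also built to coincide. It uses only ratings of 0 and 4 and needs at least six questionnaires per person; with five, a different pair is needed. It shows what can happen, not what is likely.

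A reader might further infer that unlisted reactions will go unreported. The documents do not support this. They do not say how free text will be handled, and silence is not a decision to withhold it. Staff could list the answers without a written plan.

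Finally, this is a secondary objective in a 12-person trial, and intervals around the counts will be wide. That limits the weight of the point, but the counts remain worth reporting.

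**Conclusion.** The point holds as a cheap improvement to the tolerability reporting. Two parts need no assumption: no count of participants by severity is planned, and no analysis or listing of the open-ended answers is planned. A third part is an ambiguity, since the unit of the sensation summary is not stated.

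The consequence of that ambiguity is conditional. With pooled or by-session summaries, 6 per arm and ten questionnaires each, 1 of 6 and 6 of 6 severe reactors can give identical results. With one value per participant they do not. The documents do not support saying that the plan pools sessions or that it suppresses free text. The primary efficacy analysis is unaffected.

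**What to change.** In Safety and Tolerability Endpoint, General Statistical Considerations and Primary Analyses:

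1. Make the participant the unit of the main tolerability summary. For each sensation item, take each participant's worst rating over all sessions and report by arm the number and percentage at each level from 0 to 4.
2. List every open-ended answer by arm, participant and session.
3. Keep the session-level model as supportive.

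The cost is a few lines of wording, one table and one listing, drawn from at most 12 × 10 = 120 questionnaires that are collected anyway. The small downside is that a worst rating does not show how often a sensation recurs; the retained session-level summary covers that.
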